IGT Systems	Post-Market Clinical Study Protocol DCR4Contrast Clinical Evidence Study	Doc ID: XCY612-130576 Rev: 02 Page 1 of 33
-------------	-----------------------------------------------------------------------------	--------------------------------------------------

DCR4Contrast trial

Author:

[REDACTED] Development Scientist

Department:

Clinical Science & Medical Affairs

Approval

Name	Role	Date (yyyy Mon dd)	Signature
[REDACTED]	GEN: Clinical Operations Lead	2019 Jul 09	[REDACTED]
[REDACTED]	InCs: Study Leader	2019 Jul 09	[REDACTED]
[REDACTED]	Q&R: RA Officer	2019 Jul 09	[REDACTED]
[REDACTED]	GEN: Biostatistician	2019 JUL 09	[REDACTED]

All approvers have signed. Approval and effective date is the date of the latest signature.

IGT Systems	Post-Market Clinical Study Protocol DCR4Contrast Clinical Evidence Study	Doc ID: XCY612-130576 Rev: 02 Page 2 of 33
-------------	-----------------------------------------------------------------------------	--------------------------------------------------

Revision History

Revision	Revision Date	Author	Changes/Comments
00	2018 Apr 05		Initial version
01	2019 Jun 05		
Protocol updated based on feedback from investigators and study coordinators at the potential sites:
 
 • Target patient population extended from elective PCI to elective + ad hoc PCI; rephrased inclusion/exclusion criteria, objectives, endpoints and study procedures to accommodate this change (see Summary section, Chapter 5, 6, and 7) • Chapter 9: Changed such that all (also non significant) changes of the clinical study protocol shall be notified to, or approved by the MEC and where appropriate regulatory authorities. • Appendix I: Updated list of investigators, sites, and third parties involved in the study • Appendix II: Updated list of monitors/clinical scientists, clinical study managers
02	2019 Jul 04		
Protocol updated based on FDA pre-submission meeting feedback:
 
 • The secondary objective on the iodinated contrast volume used per vessel PCI has been moved to the Exploratory objectives. • Updated the sample size justification for the secondary objective resulting in 394 subjects required for the study (360 previously). • Added site effect analysis for the primary endpoint to assess poolability of data. • Added sensitivity analysis for the primary endpoint to perform worst-case analysis for missing data.

Open Issues

None

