7.8.10. Sensitivity Analysis for the Primary Endpoint

A worst-case analysis will be considered for the primary endpoint [the average total undiluted iodinated contrast volume (in ml) used per PCI]. For missing outcomes for the control group, the lower bound of the 95% confidence interval around the control mean will be imputed. For missing outcomes for the DCR group, the upper bound of the 95% confidence interval around the DCR mean will be imputed. The primary endpoint will be re-assessed with a complete dataset.

8. Data management

An e-CRF will be used to collect medical history, subjects demographics, procedure related information, protocol deviations, adverse events and device deficiencies.

The e-CRF will be used for data review, data cleaning and issuing and resolving queries. This e-CRF is a web-based e-CRF which is password protected and is 21 CFR part 11 compliant. At the end of the study the data will be stored as a frozen dataset and will be retained. Interview can be performed separately from the e-CRF.

The e-CRF data from the subjects will be key-coded (pseudonymized). The information related to the subjects (like name) is kept separately in the enrollment log at the hospital. Date and time of the procedure and date of discharge will be collected.

All exported (image) data will be de-identified and this data will be collected and stored in a secure location.

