8.1.1 Sample Size Justification Primary Endpoint

A recent single center, non-randomized, retrospective study [Yabe 2018] has shown to achieve 21.9% contrast reduction when using Dynamic Coronary Roadmap compared to the control group without using Dynamic Coronary Roadmap, see Table 2.

	Control group	DCR group
Number of patients	103	43
Iodinated contrast volume (ml) average \pm standard deviation	152.1 ± 73.0	118.8 ± 49.7

Table 2 Results of a recent pilot study [Yabe 2018]

To determine the sample size for the primary endpoint of this study we used the Yabe study outcomes as input with a margin of 7% for the contrast reduction, i.e., the sample size calculation is performed to reliably show a 15% contrast reduction in the DCR group compared to the control group not using Dynamic Coronary Roadmap.

For the sample size and power calculations we have set:

- Estimated mean for the Control group = 152.1 (based on [Yabe 2018])
- Estimated mean for the DCR group = 129.3 (15% reduction)
- Estimated standard deviation = 73.0 (based on [Yabe 2018])
- Effect size (standardized difference): $(152.1 - 129.3)/73.0 = 0.3123$
- Significance: one-sided $\alpha = 0.025$ (the type I error, i.e., probability of rejecting a true null hypothesis)

Document ID:	<As applicable, per local requirements>	Document title:		Classification:	For internal use
		Statistical Analysis Plan			
Modified:	11MAY2023			Author:	
Version:	3.0	Template ID:	ClinicalStudyTemplate0025	Approver:	
Status:	Final	Template Version Date:	02MAR2018	Page:	21 of 52

Statistical Analysis Plan

- Power (1- β) = 80%

Sample sizes of 162 for each group achieves 80% power to reject the null hypothesis of equal means when the population mean difference is 15% with a standard deviation of 73.0 for both groups and with a significance level (alpha) of 0.025 using a one-sided two-sample equal-variance t-test (calculated by PASS 16.0.3 software).

Finally the percentage of subjects that are expected to be lost at random during the course of the study (drop-out rate) and for whom no response data will be collected (i.e., will be treated as "missing") needs to be taken into account. A drop-out rate of 10% (DR=0.1) is assumed, meaning that $162/(1-DR)=180$ patients are needed in each group totaling 360 patients for the primary endpoint.

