8.2.1 Analysis Population

The following analysis populations will be defined in this study.

Enrolled Population

The enrolled population is defined as all subjects who signed informed consent.

Randomized population

The randomised population is defined as all randomised subjects, defined as any subject with a randomisation result as recorded in the eCRF.

Analysis of data using the randomised population will consider allocation of subjects to treatment groups as randomised.

Full Analysis Population

The full analysis population (FAP) is defined as all randomised subjects who underwent a PCI in at least one vessel without the use of OCT and/or rotational or orbital atherectomy of which the primary endpoint and/or the secondary endpoint is available.

Analysis of data using the Full analysis population will consider allocation of subjects to treatment groups as randomised.

Safety population

The safety analysis population (SAF) is defined as all randomised subjects who underwent a(n) attempt to PCI or another procedure (for example CABG).

Analysis of data using the Safety population will consider allocation of subjects to treatment groups as treated (i.e. will be based on the actual treatment a subject has received regardless of which treatment they were randomised to receive).

In case the safety population is equal to the full analysis population, only the results of the full analysis population will be presented.

Per Protocol population

The Per Protocol population is defined as all FAP subjects without major protocol violations. Protocol violations are failures to adhere to the inclusion/exclusion criteria and protocol requirements and will be divided into major protocol violations and minor protocol violations. Major protocol violations are those that are considered to have a significant effect on the treatment efficacy and hence would exclude the subject from the PP population. Minor protocol violations are those that are not considered to significantly affect the efficacy evaluation and

Document ID:	<As applicable, per local requirements>	Document title:	Classification:	For internal use
Modified:	11MAY2023	Statistical Analysis Plan		
Version:	3.0	Template ID:	ClinicalStudyTemplate0025	Approver:
Status:	Final	Template Version Date:	02MAR2018	Page: 24 of 52

Statistical Analysis Plan

hence do not warrant subjects' exclusion from the PP population. Major protocol violations will be identified by a Data Review Meeting prior to database lock.

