8.2.2 Handling of Dropouts or Missing Data

We will perform a missing value analysis to check the volume of missing data and whether the missing data show patterns across subgroups. In case the missing values are non-ignorable, methods to correct for missing data will be used like, e.g., worst case scenario analysis, multiple imputation methods [Rubin 2004].

For the primary endpoint a worst-case analysis will be considered as a sensitivity analysis. For missing outcomes for the control group, the lower bound of the 95% confidence interval around the control mean will be imputed. For missing outcomes for the DCR group, the upper bound of the 95% confidence interval around the DCR mean will be imputed. The primary analysis will be repeated using the imputed values.

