The results of the t-test will be displayed as estimates of the between treatment group difference (with 95% confidence intervals) and the (one-sided) p-value for the between treatment group difference. When the p-value is lower than the significance level of 2.5% (alpha) we will reject the null hypothesis.

The primary analysis will be repeated for the PP population.

In addition and for sensitivity purposes a worst-case analysis will be considered for the primary endpoint. For missing outcomes for the control group, the lower bound of the 95% confidence interval around the control mean will be imputed. For missing outcomes for the DCR group, the upper bound of the 95% confidence interval around the DCR mean will be imputed. The primary endpoint will be re-assessed with a complete dataset for the FAP population.

As a descriptive analysis, the (V) to creatinine clearance GFR ratio will be calculated. Assuming a contrast volume reduction by DCR, the contrast volume/GFR ratio will give information on how clinically meaningful this contrast reduction is. The ratio will be calculated by dividing the volume of contrast volume (in ml) received by the patients' GFR (in ml/min/1.73m²).

Document ID:	<As applicable, per local requirements>	Document title:		Classification:	For internal use
Modified:	11MAY2023	Statistical Analysis Plan		Author:	
Version:	3.0	Template ID:	ClinicalStudyTemplate0025	Approver:	
Status:	Final	Template Version Date:	02MAR2018	Page:	29 of 52

Statistical Analysis Plan

The CKD-EPI equation to estimate the glomerular filtration rate reads [Levey 2009]:

$$eGFR = 141 * \min(SCr/K, 1)^\alpha * \max(SCr/K, 1)^{-1.209} * 0.993^{Age} * 1.018 \text{ [if female]} * 1.159 \text{ [if black]}$$

with $K=0.7$ and $\alpha=-0.329$ if female

with $K=0.9$ and $\alpha=-0.411$ if male

Here min indicates the minimum of SCr/K or 1, and max indicates the maximum of SCr/K or 1. In case the race is unknown we will use 1 as multiplication factor.

As recommended by the ESC/EACTS Guidelines, the total contrast volume/GFR ratio should not exceed 3.7, because when the ratio is larger than 3.7 the risk for severe CKD ($eGFR < 30$) increases significantly [Laskey 2007, Neumann 2018].

The average V/GFR ratio (with 95% CI) and the proportion of patients with a V/GFR ratio > 3.7 (with 95% exact CI) will be presented by treatment group for the FAP.

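### The worst-case sensitivity analysis moves missing contrast volumes only about 0.15 SD and treats the filled-in constants as real data, so it does not test a worst case (minor)

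*SAP*

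**What the plan says.** SAP 8.2.2, SAP 8.11.1 and protocol 7.8.10 give the same rule.

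- Control arm: "For missing outcomes for the control group, the lower bound of the 95% confidence interval around the control mean will be imputed".
- DCR arm: "For missing outcomes for the DCR group, the upper bound of the 95% confidence interval around the DCR mean will be imputed".
- The primary test is then repeated on the filled-in data: "The primary endpoint will be re-assessed with a complete dataset for the FAP population" (SAP 8.11.1).

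No section corrects the variance for imputation, sets a range of shifts, or uses extreme individual values. The commitment is soft: "A worst-case analysis will be considered for the primary endpoint" (protocol 7.8.10). The protocol's Revision History, cited here only for the purpose of the analysis, places it among changes made after regulator feedback: "Added sensitivity analysis for the primary endpoint to perform worst-case analysis for missing data".

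Two other provisions matter. SAP 8.2.2 plans a missing-value analysis and adds: "In case the missing values are non-ignorable, methods to correct for missing data will be used". It names worst-case analysis and multiple imputation as examples but gives no model and no size of shift. SAP 8.2.1 limits the full analysis population (FAP) to subjects "of which the primary endpoint and/or the secondary endpoint is available". The rule can therefore fill only subjects who have an angiogram count but no contrast volume.

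**The concern.** A confidence limit of a mean describes how well the mean is known, SD/sqrt(n). It does not describe how far one patient's contrast volume may lie from the average, which is the SD. With nearly 200 patients per arm the two differ by a factor of about 14 before the 1.96 multiplier. Filling in such a limit makes the missing patient close to typical.

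Giving every missing patient in an arm the same constant and re-running the t-test adds sample size but almost no variance. The information still comes from the observed patients alone, so the reported standard error is too small.

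This is the only missing-data check of the primary endpoint with a stated rule. Its label implies that adverse missingness has been explored, and it cannot show how large a departure would overturn the result.

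**Working it through.** **The plan's own figure.** Inputs from SAP 8.1.1: means 152.1 and 129.3 ml (difference 22.8), SD 73.0, one-sided alpha 0.025. The noncentral-t calculation gives 162 per arm for 80.0% power, and 162/0.9 = 180, as the SAP states. The trial size is 394, so N = 197 per arm.

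**Assumption.** The documents do not say how many values will be imputed. I use m = 3, 5 and 10 per arm, and 20 as an upper illustration only. Observed per arm: n = 197 - m.

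**Formulas.**

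- Distance from arm mean to confidence limit: h = t(0.975, n-1) × 73/sqrt(n)
- Complete cases: SE = 73 × sqrt(2/n)
- SAP rule: difference = 22.8 - 2(m/N)h; SD = sqrt{[(n-1)73² + (nm/N)h²]/(N-1)}; SE = SD × sqrt(2/N)
- Same shift by multiple imputation (100 imputations): within-imputation variance W = 2[73² + (m/N)(n/N)h²]/N; between-imputation variance B = 2(m/N)² × 73² × (1/n + 1/m); SE = sqrt(W + 1.01B)

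**Worked case, m = 5, n = 192.**

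- h = 10.39 ml = 0.142 SD.
- Complete cases: SE = 7.45, t = 22.8/7.45 = 3.060, one-sided p = 0.00118.
- SAP rule: difference = 22.8 - 2(5/197)(10.39) = 22.27; SD = 72.08; SE = 7.26; t = 3.067, p = 0.00116.
- Multiple imputation: W = 54.13, B = 1.41; SE = sqrt(54.13 + 1.42) = 7.45; t = 22.27/7.45 = 2.988, p = 0.0015.
- SE understatement: 1 - 7.263/7.453 = 2.6%.

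| Imputed per arm | h, ml (SD) | Difference under rule, ml | SE: rule / multiple imputation | SE too small by | p: complete cases / rule / multiple imputation |
|---|---|---|---|---|---|
| 3 | 10.34 (0.142) | 22.49 | 7.30 / 7.41 | 1.5% | 0.00112 / 0.00111 / 0.0013 |
| 5 | 10.39 (0.142) | 22.27 | 7.26 / 7.45 | 2.6% | 0.00118 / 0.00116 / 0.0015 |
| 10 | 10.53 (0.144) | 21.73 | 7.17 / 7.55 | 5.1% | 0.00135 / 0.00130 / 0.0021 |
| 20 (illustration) | 10.83 (0.148) | 20.60 | 6.98 / 7.77 | 10.2% | 0.00176 / 0.00167 / 0.0042 |

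A simulation of the rule (40,000 trials) gave reported SE over true SD of the estimate of 0.98, 0.95 and 0.90 for m = 5, 10 and 20, in agreement.

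**When the rule lowers p.** The smaller SE offsets the shift only if the complete-case t is about 2.8 or more, an observed reduction of roughly 14%. Below that the rule raises p.

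**When the variance error would change the verdict.** The rule and the multiple-imputation version disagree only if the complete-case p lies in 0.0226-0.0243, 0.0211-0.0238 or 0.0178-0.0227 (m = 3, 5, 10). At the planned effect the chance of that is about 0.7%, 1.2% or 2.5%.

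**Shift needed to overturn the planned result.** Solving for multiple-imputation p = 0.025, with missing control values moved down and missing DCR values up by the same amount, gives about 235, 147 and 75 ml (m = 3, 5, 10), against the 10 to 11 ml tried. The first two are not plausible. At m = 3 the mean imputed control volume would be 152.1 - 234.8 = -82.7 ml. At m = 5 it would be 152.1 - 146.8 = 5.3 ml, with about 47% of normal draws (SD 73) below zero.

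**Log scale.** The SAP 11 table list has the primary analysis on log-transformed volume. Assuming lognormal data with log SD 0.455 and a 15% reduction, m = 5 gives p = 0.00026, 0.00025 and 0.00034 in the same order, with the same 2.6% SE understatement.

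**The case against.** The strongest reply is that little depends on this. Contrast volume is read from the injector during the procedure, so no later visit is needed and few values should be missing. At 3 to 5 per arm the SE error is 1.5% to 2.6% and p hardly moves. That stands, and it is why the point is minor.

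A reader might take the 10% drop-out allowance to mean about 20 imputed per arm and a 10% SE error. The documents do not support that. SAP 8.1.1 defines those drop-outs as subjects "for whom no response data will be collected", and subjects with neither endpoint are outside the FAP and are never imputed.

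A reader might also infer that the plan has no other provision for missing data. It has one: SAP 8.2.2 commits to examining missingness and to correcting for it if it is non-ignorable. But observed data alone cannot settle that condition, and no model or shift is given. The rule with a stated recipe therefore remains the working check.

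It can be said that the complaint is about a label, since the rule is stated openly and SAP 8.11.1 reports the number with non-missing data. In part it is. The understated SE is a defect whatever the name.

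Finally, an unbounded search for a tipping point on the raw scale would end at impossible volumes when few values are missing. That is correct, and the fix is bounded for this reason.

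**Conclusion.** The concern holds as a minor one. The rule as written does not do what its label says: it shifts missing values by 0.14 to 0.15 SD and understates the SE by about 1.5% to 5% with 3 to 10 imputed per arm. Only the point estimate always moves toward the null. The p-value need not rise, and at the planned effect it falls very slightly.

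Two stronger inferences should be resisted. The analysis does not put the primary result in doubt: the primary test, alpha and power do not depend on it, and every planned-effect p-value in the table is far below 0.025. Nor does the rule always favour DCR; below a complete-case t of about 2.8 it raises p.

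The figures rest on the planning means and SD, 197 per arm, equal numbers missing in each arm, normal data (with the log-scale check above), and assumed numbers imputed.

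**What to change.** In SAP 8.2.2 and 8.11.1:

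- Drop the worst-case label. The current fill may stay under a plain name such as confidence-limit imputation.
- State that a tipping-point analysis will be performed, not merely considered. Use delta-adjusted multiple imputation by arm, with residual variance and Rubin's rules, on the scale of the primary analysis (raw or log).
- Move missing control values down and missing DCR values up in steps, within plausible volumes. Allow no negative imputed volume, either by working on the log scale or by stopping at the observed range.
- Report the shift at which one-sided p exceeds 0.025, or that no plausible shift overturns the result, with the number imputed per arm (FAP size minus the non-missing n).

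List the change in SAP 9.2, and either align protocol 7.8.10 or document a justified deviation as protocol section 7 allows. Subjects missing both endpoints raise a separate question about the FAP definition and are best dealt with there.

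The cost is a few sentences and a short program, with no new patients or data and no change to the primary test. The downside is that the sensitivity result may look less favourable. The benefit may go the other way: with very few missing values, the report could state that no plausible shift overturns the result, which the present rule cannot show.

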8.11.2 Secondary Efficacy Analysis

The secondary endpoint is the average total number of contrast enhanced cine angiographic X-ray runs (angiograms) per PCI (from first positioning the interventional guiding catheter in stable coronary position till end of PCI procedure) determined via visual assessment (e.g., on the Philips X-ray system To assess the total number of contrast enhanced cine angiographic X-ray runs (angiograms) related to PCI in the Dynamic Coronary Roadmap and control group

Hypothesis

Dynamic Coronary Roadmap reduces the total number of contrast enhanced cine angiographic X-ray runs (angiograms) acquired on average per PCI. The null and alternative hypotheses are as follows:

$$H_0: Pop_{Control2} \leq Pop_{DCR2}$$

$$H_a: Pop_{Control2} > Pop_{DCR2} \text{ (Distribution of Control is shifted to the right of DCR)}$$

Where $Pop_{Control2}$ is the population distribution for the number of contrast enhanced cine angiographic X-ray runs (angiograms) acquired per PCI for the Control group, and Pop_{DCR2} is the population distribution for the number of contrast enhanced cine angiographic X-ray runs (angiograms) acquired per PCI for the DCR group.

Document ID:	<As applicable, per local requirements>	Document title:		Classification:	For internal use
		Statistical Analysis Plan			
Modified:	11MAY2023			Author:	
Version:	3.0	Template ID:	ClinicalStudyTemplate0025	Approver:	
Status:	Final	Template Version Date:	02MAR2018	Page:	30 of 52

Statistical Analysis Plan

Analysis

Descriptive summaries of the total number of contrast enhanced cine angiographic X-ray runs (angiograms) will be presented by treatment group for the FAP and the PP population and will include the number of subjects with non-missing data (n), frequency distributions, median, interquartile range (IQR) and minimum and maximum values.

The number of angiographic X-ray runs is discrete and is likely to be not normally distributed, so the endpoint will be evaluated using a one-sided Wilcoxon-Mann-Whitney test. The results of the Wilcoxon-Mann-Whitney will be displayed as the rank sum and the (one-sided) p-value for the between treatment group difference. When the p-value is lower than the significance level of 2.5% (alpha) we will reject the null hypothesis.

All subjects in the full analysis population will be included in this analysis. The secondary analysis will be repeated for the PP population.

8.11.3 Exploratory Efficacy Analysis

8.11.3.1 Contrast Volume per Vessel PCI

The average undiluted iodinated contrast volume (in ml) used per vessel PCI (from first positioning the interventional guiding catheter in stable coronary position till end of PCI procedure) by treatment group. For multi vessel PCI the iodinated contrast volume used per vessel PCI will be determined based on the total PCI contrast volume (from first positioning the interventional guiding catheter in stable coronary position till end of PCI procedure) divided by the number of vessels actually treated by PCI.

Descriptive summaries of the total undiluted iodinated contrast volume divided by the actual number of vessels treated by PCI will be presented by treatment group for the FAP and the PP population and will include the number of subjects with non-missing data (n), mean with 95% confidence interval, standard deviation (SD), median, interquartile range (IQR) and minimum and maximum values.

The endpoint will be evaluated using a one-sided two-sample t-test. We will test for assumptions, e.g. normality and equal variances. Normality will be checked using histograms and Q-Q plots. If there are strong indications of non-normality, the data will be (log)transformed, and the back transformed results will be presented. Levene's test for equality of variances will be applied. When the p-value of this test is greater than 0.05, then we assume the variances are equal and we will use the arithmetic mean of the variances in calculating the standard error. When the p-value is less than or equal to 0.05, then we assume

Document ID:	<As applicable, per local requirements>	Document title:		Classification:	For internal use
		Statistical Analysis Plan			
Modified:	11MAY2023	Template ID:	ClinicalStudyTemplate0025	Author:	
Version:	3.0	Template Version Date:	02MAR2018	Approver:	
Status:	Final			Page:	31 of 52

Statistical Analysis Plan

the variances are unequal and then we will calculate the standard error from the weighted average of the two variances.

The results of the t-test will be displayed as estimates of the between treatment group difference (with 95% confidence intervals) and the (one-sided) p-value for the between treatment group difference. When the p-value is lower than the significance level of 2.5% (alpha) we will reject the null hypothesis.

All subjects in the FAP population will be included in this analysis. The analysis will be repeated for the PP population.

